Specific aims: **1)** Determine if dyads in the TIP-C+SMSH as compared to the SMSH alone group created by the first randomization will have: a) lower depression, anxiety, and summed severity of 13 other symptoms at weeks 1-12, 13, and 17 (primary outcomes); b) lower use of healthcare services (hospitalizations, urgent care or emergency department [ED] visits) during 17 weeks (secondary outcomes); c) greater self-efficacy, social support, and lower caregiver burden during weeks 13 and 17 (potential mediators). **2)** Among nonresponders to the SMSH alone after 4 weeks, determine if dyads assigned to TIP-C+SMSH as compared to the SMSH alone group created by the second randomization will have better primary and secondary outcomes and potential mediators at weeks 5-12, 13, and 17. **3)** Test the interdependence in survivor's and caregiver's primary and secondary outcomes. **4)** Determine which characteristics of the dyad are associated with responses to the SMSH alone during weeks 1-4 and optimal outcomes for the dyad during weeks 1-12, 13 and 17 so as to determine tailoring variables for the decision rules of individualized sequencing of interventions. Findings will be used to improve symptom management and reduce distress in survivor-caregiver dyads.

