Sample size and power considerations. To determine sample size, we started at the right of the schematic in Figure 1 (the second randomization) and moved from right to left to determine the needed number of consenting dyads. To power the comparisons on primary outcomes for the groups created by the second randomization (Aim 2), we used the effect size of Cohen’s $d=0.39$ (adjusted for baseline), the smallest seen in the preliminary data for TIP-C against an educational intervention (Table 1) to conservatively estimate sample size requirements. We further adjusted this effect size for the reduction in error variance due to 10 repeated measures of primary outcomes. In past studies, Pearson correlation coefficients between pairs of repeated measures of depression, anxiety and summed severity of other symptoms ranged from $r=0.36$ to 0.77, resulting in the range of the adjusted effect sizes from $d=0.54$ to 0.84. Using the smallest adjusted $d=0.54$, the required sample size is 60 per group created by the second randomization, for power of .80 or greater in two-tailed tests at the 0.05 level of significance.

Moving from left to right in Figure 1 (schematic), 120 dyads from two groups created by the second randomization will be non-responders to the SMSH alone. From past work, response rate to the SMSH on depression and anxiety was approximately 30%,²²⁸ therefore 120 non-responders will be 70% of 172 randomized to the SMSH alone in the first randomization. The comparison of these 172 to 60 dyads allocated to the TIP-C+SMSH in the first randomization will have power of 0.95 to detect the effect size of 0.54 (adjusted for the repeated measures) in testing the hypothesis associated with Aim 1. The tests of mediation and interdependence effects in Aim 3 will have an even greater power because of further reduction in error variance. Aim 4 is exploratory, thus formal power considerations are not applicable. In summary, the total

required post-attrition sample size for all specific aims is N=232. To account for 22% attrition based on past work, we will need 298 dyads to consent.

Recruitment and retention of participants.

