
Design. We selected the SMART design (Figure 1) for this study over alternative designs (e.g., implementation designs) because the SMART design allows a precision or personalized approach to determine the right treatment at the right dose with the right sequence for the right survivor-caregiver dyad. SMART designs, although newer, show promise in developing the sequences of evidence-based interventions for more efficient and individualized patient- and caregiver-centered care. We will use findings from this study to create an algorithm for clinically meaningful decision making about symptom management for survivors and their caregivers to be tested in future implementation/dissemination studies. We will recruit 298 cancer survivors undergoing chemotherapy, targeted therapy, or hormonal therapy for a solid tumor at the NCI designated University of Arizona Comprehensive Cancer Center (UACC, Tucson and Phoenix locations) and at Arizona community oncology settings. The survivors will be screened for moderate or severe depression and/or anxiety prior to enrollment and identify the informal caregivers who will participate in the study. Following enrollment, informed consent and baseline interview of both survivor and caregiver, the dyad will be randomly assigned to either: 1) SMSH alone or 2) TIP-C+SMSH for 8 weeks followed by continued SMSH alone for 4 weeks. During 12 weeks following initial randomization, all participants will receive weekly telephone contacts to assess symptoms, deliver the assigned intervention and assess its enactment and fidelity. After the initial 4 weeks in the SMSH alone group, the survivor’s response to the intervention will be determined. If the survivor responds (defined as a reduced score on depression and/or anxiety) (See C9a. Primary Outcomes), the dyad will continue with the SMSH alone for 8 more weeks. If the survivor is a non-responder (defined as no improvement or a worsening score for depression and/or anxiety), the dyad will be re-randomized to either continue with SMSH alone for 8 more weeks, or add 8 weeks of TIP-C. The rationale for using the survivor’s response as the criterion for re-randomization is from the extensive evidence of interdependence in survivor and caregiver outcomes presented, and on the caregiver’s focus on the survivor’s outcomes. The rationale for timing of the assessment of response and re-randomization to add the TIP-C intervention after 4 weeks is based on past testing of the SMSH,^{15,16,30} where median time to response on psychological distress ranged from 14 to 24 days. Post-intervention and follow-up telephone assessments are at weeks 13 and 17.

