Secondary outcomes. Secondary outcomes are caregivers' and survivors' hospitalizations, urgent care or ED visits during the study. In baseline, week 13 and 17 interviews over the telephone, each dyad member will be asked to recall ED visits and admissions to hospitals and, if they occurred, their reasons and duration. Recall period will be 3 months in baseline and week 13, and 1 month in week 17 interviews. Extensive previous research²⁻⁵ documents self-report is a reliable and valid method to collect health services use data especially when standardized methods are used and the recall period is short, as in this project. Self-report is the only reasonable and cost-effective way to assess healthcare use, as it would be impossible to access health (medical) records across the multiple systems and payers used by participants in this study.

Potential mediators.

Caregivers' and survivors' self-efficacy. PROMIS 4-item short forms (sf) will be administered in interviews.²⁵³⁻²⁵⁶ Self-efficacy specific to symptom management will be captured by the GSDS item described above.

Caregivers' and survivors' social support. PROMIS 4-item-sf for emotional support and PROMIS Informational Support 4a will be used in interviews.²⁵³⁻²⁵⁶

Caregiver Reaction Assessment Tool.²⁵⁷ This caregiver burden tool was developed and validated with caregivers of patients with chronic conditions. It has 5 subscales: impact on schedule, caregiver's esteem, family support, impact on health, and impact on finances, with Cronbach's alphas exceeding 0.70.

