6. Identification of Adverse Effects- The following will be considered serious adverse events (SAE): death, attempted suicide, major depression, breach of confidentiality. Death, attempted suicide and major depression would not occur as a direct result of study interventions, however, could be encountered during implementation of this study due to the inclusion criteria of cancer survivors. A breach in confidentiality may result from participation in this study. The investigators have successfully trained staff to monitor and protect confidentiality of participants in large research studies conducted over the past two decades. Similar training strategies will be incorporated for training of staff in this study. Additionally, all research staff will complete the human subjects and HIPAA certification training.

The following will be considered adverse events (AE): severe symptoms requiring hospitalization or urgent care. Again, severe symptoms are not expected to result from participation in this study but may result from cancer, its treatment or other existing comorbid conditions.

Averse events and serious adverse events may be identified during implementation of the experimental protocols and are monitored by the Investigators in several ways.

Interviewers: Interviewers may identify both serious adverse events and/or adverse events

during completion of telephone interviews or telephone calls to schedule telephone interviews. **Interventionists:** The interventionists may identify both serious adverse events and/or adverse events during their telephone contacts with the participants.

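### Health service use is recalled only over fixed windows at weeks 13 and 17, so use before dropout, and most of the 17 weeks when week 13 is missed, is never asked about

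*Combined protocol and SAP*

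**What the plan says.** Section 2.0 states the Aim 1 secondary outcome as "lower use of healthcare services (hospitalizations, urgent care or emergency department [ED] visits) during 17 weeks (secondary outcomes". Section 6.0 (Secondary outcomes) gives the data source: "In baseline, week 13 and 17 interviews over the telephone, each dyad member will be asked to recall ED visits and admissions to hospitals". It then sets the windows: "Recall period will be 3 months in baseline and week 13, and 1 month in week 17 interviews". The baseline window precedes randomization, so on-study use rests on the week-13 and week-17 interviews alone.

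The same paragraph rules out records as a source for this outcome: "it would be impossible to access health (medical) records across the multiple systems and payers used by participants in this study". The health record audit described elsewhere in Section 6.0 concerns survivors' treatment, cancer site and stage, and medications.

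Both dyad members are also called every week for 12 weeks. Section 5.0 describes those calls: "all participants will receive weekly telephone contacts to assess symptoms, deliver the assigned intervention and assess its enactment and fidelity". Health service use is not listed there or in the call descriptions in Section 7.0. Section 10.0 offers partial overlap through safety reporting: "The following will be considered adverse events (AE): severe symptoms requiring hospitalization or urgent care". It says staff may identify such events during calls, but does not name them as a source for the secondary outcome.

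Section 8.0 analyses the counts in repeated-measures models (Poisson, zero-inflated Poisson or negative binomial) with time as a class variable. The missing-data text is general: intent to treat, regression valid under MAR, attrition compared between groups, and pattern-mixture models and sensitivity analyses if NMAR is suspected. No section provides an interview at withdrawal or a longer recall window after a missed interview.

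**The concern.** Two fixed windows placed end to end leave almost no slack. Whatever is not asked at week 13 is not asked again at week 17. What staff could have learned in weekly calls before dropout is not collected as an outcome.

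The loss may also be selective. A survivor who is in hospital or very ill may miss the week-13 interview or leave the study for that reason, so the same illness can produce both the event and the missing count. MAR is then less secure for this outcome than for the symptom scores, which are collected weekly and so leave data up to the point of dropout. At stake are the absolute rates of service use, the precision of the group comparisons and, under some conditions, the validity of those comparisons.

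**Working it through.** **The plan's own figure.** Section 4.0 states: "To account for 22% attrition based on past work, we will need 298 dyads to consent". From 232 analysable dyads, 232 / (1 − 0.22) = 297.4, rounded up to 298. This reproduces. Expected loss is 298 − 232 = 66 dyads, and 66 / 298 = 22.1%.

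**Window lengths.** A month is 365.25 / 12 days.
- Week-13 window: 3 months = 3 × 365.25 / 12 / 7 = 13.04 weeks.
- Week-17 window: 1 month = 4.35 weeks.
- Sum: 13.04 + 4.35 = 17.39 weeks, for an outcome period of 17 weeks.

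**Coverage by interview pattern.**
- Both interviews on time: all 17 weeks covered.
- Week 13 done, week 17 missed: about 4 of 17 weeks lost (24%).
- Week 13 missed, week 17 done: 4.35 weeks covered; 17 − 4.35 = 12.65 weeks lost, and 12.65 / 17 = 74%.
- Neither done: 0 of 17 weeks covered, whatever the number of weekly calls answered.
- Week-13 interview held at week 15 (an example; Table 4 in Section 9.0 gives no visit windows): recall starts at 15 − 13.04 = week 1.96, so about the first two weeks are missed. The week-17 window starts at 17 − 4.35 = week 12.65, so the two windows overlap by 15 − 12.65 = 2.35 weeks, and an event in that stretch could be reported twice.

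**Unobserved person-time across the trial.** Total: 298 × 17 = 5,066 dyad-weeks. The documents do not give the timing of the 66 losses, so let s be the share leaving before week 13. Assume that those who leave earlier complete neither interview, that those who leave later complete week 13 only, and that both members of a dyad are lost together. Unobserved time = 66 × s × 17 + 66 × (1 − s) × 4.

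| s | Dyad-weeks unobserved | Share of 5,066 |
|---|---|---|
| 0% | 264 | 5.2% |
| 50% | 561 + 132 = 693 | 13.7% |
| 100% | 1,122 | 22.1% |

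**How much of this a weekly item could recover.** Only time before dropout. If dropout were uniform over weeks 0 to 13 (an assumption), the mean is 6.5 weeks per early dropout, or 6.5 / 17 = 38% of that person's period. At s = 50% this is 33 × 6.5 = 214.5 dyad-weeks (4.2% of the total); at s = 100% it is 66 × 6.5 = 429 (8.5%). The rest is ordinary loss to follow-up.

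**The case against.** **The count model needs no offset as it stands.** A reader might infer that omitting an exposure offset is itself an error. The documents do not support that. The model does not analyse one 17-week total: weeks 13 and 17 are separate repeated measures, and time is a class variable. With a log link and a fixed window at each interview, the window length is constant within each time level and the time effect absorbs it. A missed week 13 is then a missing repeated measure, and the week-17 count is valid for its own month. A late week-13 interview still has three months of exposure; only the weeks covered shift. This part of the objection stands.

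**The missing-data plan addresses selective loss.** It does in part: attrition is compared between groups, and pattern-mixture and sensitivity analyses are foreseen. These can model the loss but cannot supply events that nobody asked about.

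**Little loss or imbalance is expected.** Section 8.0 (Potential Difficulties) reports high past retention without differential attrition. A reader might still go further and infer a definite bias. For example, if all 66 lost dyads leave before week 13 and use services at twice the completers' rate, the captured rate is too low by 1 − 1 / (0.78 + 0.22 × 2) = 1 − 1 / 1.22 = 18%. With 15% versus 25% attrition by arm, a true rate ratio of (0.85 + 0.15 × 2) / (0.75 + 0.25 × 2) = 1.15 / 1.25 = 0.92 would appear as 1.00. The documents give neither the timing nor the doubled rate, and they do not expect the imbalance. Both figures also credit dropouts with use after they left, which no change to recall would capture.

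**Weekly scripts may already ask.** The call scripts and forms are listed in Section 14.0 but not reproduced, so this cannot be excluded. The protocol text neither lists such an item nor links one to the outcome.

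**Short recall is deliberate.** Section 6.0 favours it for accuracy and wants a low respondent burden. That is a fair reason for short windows, but not for leaving a missed window unasked.

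**Conclusion.** The concern holds as a gap in data collection. Followed as written, the plan records no on-study service use for a participant who completes neither post-baseline interview, and never asks about 74% of the 17 weeks when week 13 is missed and week 17 is completed. Unobserved person-time is between about 5% and 22%, depending on when the expected 22% attrition occurs, which is not stated.

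Absolute rates and precision suffer in any case where those lost differ from those observed or simply go uncounted. The comparison between arms is biased only if the loss, or the excess use among those lost, differs by arm; the documents do not show that it will.

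This concerns a secondary outcome. Sample size and primary-outcome power rest on the symptom measures and are unaffected. The change is worth making because it is cheap and because events not asked about during the trial cannot be recovered by analysis afterwards.

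**What to change.** 1. **Anchor the recall.** At week 13, ask about use since randomization. At week 17, ask about use since the last completed interview, going back to randomization if week 13 was missed. Record the date of each event, so that a late interview leaves no gap and no event is counted twice. Dates would also let the Aim 2 analysis separate use before and after the second randomization.
2. **Add one weekly item.** In the calls already made to both members in all arms, ask a dated yes/no question on hospital, ED or urgent care use since the last call, and name it as a source for the secondary outcome. Events before dropout are then kept and ascertained in the same way in every arm.
3. **Adapt the count models.** Changes 1 and 2 make covered time unequal between participants, so include log(weeks covered) as an offset and include partial follow-up. The offset belongs with these changes and is not needed under the present fixed windows.

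Cost: reworded interview questions, slightly longer weekly calls and a line in the analysis plan. The downside is recall of up to 17 weeks for those who missed week 13, which is less exact than a short recall but better than no data. Use after dropout would still not be captured, so the missing-data sensitivity analyses remain necessary.

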7.0 DETAILED DESCRIPTION OF INTERVENTION

Describe in detail for intervention studies or indicate otherwise by checking below:

Interventions. We deliver interventions via the telephone (see section C2e for rationale) at convenient times for both the survivor and caregiver, including evenings and weekends.

Symptom Management and Survivorship Handbook (SMSH) is an evidence-based self-care management guide specific to each symptom.⁸⁴⁻⁸⁷ Each module is presented in an identical format (frequently asked questions): what the symptom is, how people describe the symptom, the causes of the symptom including medications, and a set of

strategies presented in bullet points for managing the symptom. For each symptom, there are indications as to when and for what reasons to contact the oncology practice; other resources for management are listed. The previously tested English version will be translated into Spanish using an adaptation of Brislin's translation/back translation process²⁴⁰ used by this team in the past. [name], Director of the Undergraduate Translation and Interpretation Program at the University of Arizona, will oversee the translation. Cultural experts will perform back translations of a random sample of pages from the SMSH for comparison to the original English language versions, and all discrepancies corrected between the back translated and original English language pages. Finally, a focus group of six Spanish-speaking Latinos will discuss the translation in terms of understandability (language level and complexity), use of idioms, and consistency of meaning. Focus group data will be used to finalize the SMSH translation and layout (i.e. design).

Survivors and caregivers will be mailed the Handbook in the participant's preferred language following the baseline interviews. During each week, staff will call the survivors and then their caregivers. The call will begin with the assessment of symptoms using the General Symptom Distress Scale (GSDS, described in measures). For each symptom rated at 4 or higher on a 0-10 scale of severity, the survivors will be referred to the SMSH for

symptom self-management. The threshold of 4 was selected based on the NCCN guidelines for symptom monitoring and management⁸³ and used successfully in past work.^{75,76,81,82,89} During weeks 2-12, the survivor's calls will begin with assessing SMSH use since the last call (intervention enactment), followed by the administration of the GSDS and referral to the SMSH. During weekly calls to caregivers, symptoms will also be assessed using GSDS. The caregivers will be notified of any current symptoms above threshold experienced by survivors and directed to the SMSH to assist the survivors in intervention enactment. Sharing symptom information between survivor and caregiver will be part of the informed consent. During weeks 2-12, the caregiver's calls will begin with assessing SMSH use for the management of survivors' symptoms, followed by the GSDS, summary of survivors' symptoms and referral to the SMSH. Calls will last about 10 minutes.

Table 2: TIP-C Intervention for Survivors and Informal Caregivers

| | |
|---|--|
| 1 | Introduction to protocol. Counseling, symptoms of depression, anxiety, stress, psycho-education, interpersonal formulation (session slightly longer). |
| 2 | Symptoms and interpersonal relationships, communication with key targets, modeling of communication processes with informal caregiver (IC) and health care providers (HCP). |
| 3 | Role transitions, effective social skills for coping/adapting to cancer, role playing interpersonal interactions: IC & HCP, accessing resources |
| 4 | Role disputes/role transitions, focus on communication with IC & HCP. Homework activity will focus on communication, developed individuality for each participant and completed between sessions. |
| 5 | Review homework assignment. Problematic communication patterns with others, role modeling successful communication with others. |
| 6 | Social support, barriers to seeking and securing social support. Homework assignment is an individualized activity with the IC. |
| 7 | Progress with cancer treatment. Review homework assignment. Stress and coping strategies, sources of satisfaction. Homework assignment: Increasing pleasant events. |
| 8 | Termination of counseling, review successes, reviews social support, stress and coping strategies. Future planning recommendations for follow-up treatment (e.g. antidepressants or continued counseling), framing successes and failures. Discuss options and referrals as needed. Resources available locally and nationally for survivors and their families, including financial, insurance ¹⁷² and legal information ¹⁷³ (session slightly longer). |

Telephone Interpersonal Counseling Intervention (TIP-C). Social work counselors with a master's degree and behavioral health and oncology expertise will deliver the 8-week TIP-C intervention (Table 2).

During weekly contacts, the counselors target social support behaviors using interpersonal communications techniques. Interpersonal communication facilitates processing stressful affective reactions to a cancer diagnosis and treatment, marshalling instrumental support for assistance with roles and functions, informational support for advice and information, and appraisal support for gauging and adjusting to the stressor. Counselors can personalize the counseling intervention for the specific needs or interests as expressed during sessions while still adhering to a structured protocol. For example, one survivor may need to focus on depression and family issues (e.g., role transitions such as job loss) rather than on anxiety and resource issues (e.g., transportation, lack of insurance). This approach is consistent with survivorship care recommendations²⁴¹ and recent evidence showing that improved psychological well-being occurs when an intervention addresses practical resource needs.²⁴²

Each survivor and caregiver receiving the TIP-C+SMSH intervention will receive one 40-minute telephone call per week for 8 weeks (8 sessions). The first 10 minutes of the call will follow the SMSH only intervention procedures (see C8c). The next 30 minutes will be devoted to the delivery of TIP-C. The TIP-C sessions will incorporate the symptoms assessment performed at the beginning of the call as follows: discussion of depression, anxiety and stress per protocol and referral to the SMSH for symptoms. The final 4 weeks will be SMSH only. The TIP-C intervention protocol is the same for both survivor and caregiver, the same counselor will be assigned to both members of the dyad and sessions conducted in either Spanish or English.

Counselors call the survivor and caregiver at separate convenient times to ensure they have adequate time and privacy to participate. Numerous interventions for cancer survivorship use individually delivered methods²⁴³⁻²⁴⁵ as we will use in this study. Dyadic delivery (i.e., both present at the same time) is not required and separate delivery resolves two major obstacles associated with delivering TIP-C to both members simultaneously. 1) Participants may be unwilling to discuss certain issues when the other dyad member is present such as discussing concerns that they have about each other. In such cases, the counselor can be an effective bridge between the two. Other times, participants may wish to discuss personal concerns (e.g., survivor dying). 2) Scheduling and technological difficulties multiply when both members must speak on the phone with a third party at the same time.

Training and intervention fidelity. Intervention protocol fidelity will be assured using established methods outlined by the NIH Treatment Fidelity Workgroup on consistency in dose, providers, delivery, and receipt of the intervention.²⁴⁶ TIP-C interveners will receive 24 hours of education, augmented by additional books and articles, about cancer diagnosis and treatment, psychological distress, and interpersonal counseling techniques with training protocols from previous studies.^{41,205,209,247} Counselors will listen to 8-10 hours of counseling sessions recorded for training purposes. [name] will conduct training that will continue until the counselor is rated as achieving > 90% on protocol implementation. Annual re-training occurs throughout the study.

The intervention fidelity protocols used in past studies will be used in this study. All sessions will be digitally recorded and about 10% randomly reviewed throughout the study to maintain quality, with written and verbal feedback given to the counselors. [name] will supervise the intervention quality control activities. Through weekly case supervision, we will maintain fidelity of the intervention and counselor adherence to protocols. We will evaluate adherence (number required elements discussed/ total number of elements).^{142,153,206} [name] will listen to all sessions in English from the first 5 dyads (40 hours of supervision) and then randomly review 10% of sessions throughout the study. A bilingual counselor will review sessions in Spanish using established protocols as in past studies. No one with less than 90% adherence will receive new cases until retraining has occurred, and [name] will assume responsibility for those existing cases. Following retraining, 5 dyads will be monitored to ensure that >90% adherence is achieved and then we will return to randomly selected monitoring for quality control. Anyone unable to adhere to the standardized protocols after a second retraining will be replaced.

Intervention reproducibility. Interventions must be standardized, yet the complexities of symptom distress demand a flexible approach to preserve the relevance of TIP-C for the individual. We will determine the amount of elements personalized to the specific needs of the individual within the structured protocol (number of personalized elements/ total number of elements). We will then examine the effect of personalization (e.g., more discussion of socioeconomic needs with one participant vs. another), if any, on outcomes. Counselors will keep detailed field notes after each session assessing intervention length, rapport, responsiveness, topics discussed, homework completed and satisfaction. Our past adherence rate of >85% far exceeds the rate

reported for community mental health patients who return for face-to-face appointments.²⁴⁸ Participants who miss sessions (occurrence is rare) will be rescheduled, as we will obtain multiple points of contact (e.g., home, cell, work telephone, e-mail address). If we fail to contact within the week, we will schedule the following week. We will also send an e-mail, text, or letter asking the participant to call us. Attrition rates and reasons will be documented, including being unable to reach the survivor or the caregiver or expressed desire to discontinue.

